8.3.4 Removal of Patients From Therapy or Assessments

8.3.4.1 Patient Discontinuation/Withdrawal From the Study

Patients may be withdrawn from the study for any of the following reasons:

- Patient request.
- Patient non-compliance with the study protocol.
- Use of non-permitted concurrent therapy.
- Lost to follow-up.
- Occurrence of adverse events (AEs) not compatible with the continuation of patient participation in the study, in the investigator's opinion, or unacceptable to the patient to continue.
- If the pre-infusion ECG QTcF is above 450 ms the infusion with the IMP should not be initiated and the patient should be registered as an Early Termination.
- Investigator request.
- Request by Acesion Pharma.

Patient replacement

- Patients who spontaneously convert to SR before randomisation are screen failures. Re-screening of such patients is not allowed.
- Patients who spontaneously convert to SR after randomisation and before infusion start are considered dropouts and will be replaced.
- Patients who have a QTcF above 450 ms at pre-infusion.
- Patients who do not meet inclusion criterion #2 (clinical indication for cardioversion of AF) will be replaced. Patients who stop study drug for any other reason will not be replaced.

Patients are free to withdraw from the study at any time without providing reason(s) for withdrawal and without prejudice to further treatment. The reason(s) for withdrawal will be documented in the electronic case report form (eCRF).

Patients withdrawing from the study will be encouraged to complete the same final evaluations as patients completing the study according to this protocol, particularly safety evaluations. The aim is to record data in the same way as for patients who completed the study.

Reasonable efforts will be made to contact patients who are lost to follow-up. These efforts must be documented in the patient's file.

Acesion Pharma has the right to terminate the study at any time in case of serious AEs (SAEs) or if special circumstances concerning the investigational product or the company itself occur making further treatment of patients impossible. In this event, the investigator(s) will be informed of the reason for study termination.

8.3.4.2 Treatment Discontinuation (Stop of Infusion)

The planned duration of drug infusion is described in [Section 8.4.1](#).

Criteria for stop of drug infusion prior to cardioversion or prior to the infusion duration of 30 min are as follows:

- Developing hemodynamic instability (drop in BP, drop in heart rate, unless caused by conversion) including but not limited to
 - systolic BP decrease to <90 mm Hg or significant decrease from baseline (e.g. >40 mm Hg), or mean BP decrease <70 mm Hg (calculated as [systolic BP + 2 × diastolic BP] / 3).
 - systolic BP increase to >190 mm Hg or
 - heart rate <40 bpm or
 - intolerable side effects.
- Developing changes in ECG variables (compared with pre-infusion ECG):
 - QRS +50% and/or development of BBB.
 - QTcF +60 ms.
 - QTcF >500 ms.
- Developing tremors (involuntary, rhythmic muscle contraction leading to shaking movements in one or more parts of the body)
- Per investigator decision, when it is not in the patient's best interest to continue infusion. Specific attention should be paid to any other AEs related to the central nervous system and/or any local infusion site reactions.

Pregnancy

Patients will be instructed that known or suspected pregnancy occurring during the study, in female patients or female partners of male patients, should be confirmed and reported to the investigator. The investigator should also be notified of any pregnancy occurring during the study but confirmed only after completion of the study. In the event that a patient is subsequently found to be pregnant after inclusion in the study, any pregnancy will be followed to term, and the status of mother and child will be reported to Acesion Pharma after delivery.

Full details will be recorded in the eCRF and a pregnancy reporting form will be completed (see [Section 10.1.3.1.1](#)).

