- d Haematology parameters include haemoglobin, haematocrit, red blood cells (erythrocytes), white blood cells (leukocytes, total and differential), basophils, eosinophils, lymphocytes, monocytes, neutrophils, and platelets.
- e Additional haematology and clinical chemistry parameters will be evaluated if not already assessed <72 h before start of infusion.
- f Clinical chemistry parameters include ALT, AST, bilirubin creatinine, GGT, glucose (random), and eGFR.
- g Only one coagulation parameter (either INR or APTT) is required for an individual patient. The same coagulation parameter should be consistently analysed throughout the study in an individual patient.
- h Patients with low potassium levels at screening may be supplemented with potassium. A retest is required before randomisation.
- i To be repeated for all patients on heparin or vitamin K antagonists when screening >24 h before start of infusion.
- j If TSH levels were tested within 1 week before randomisation at a local laboratory certified for the study, those results will be acceptable and should not be re-tested at screening.
- k Randomisation must occur as soon as possible between 3 h and 7 days (inclusive) after start of the current AF episode. Each randomised patient will be assigned a patient number. Note, if the patient is found eligible, the randomisation should be planned in such a way that all logistics will occur in the protocol-specified timeframes including timely reconstitution of study drug, infusion start and, if applicable, direct-current cardioversion in non-responders.

- 1 Study drugs must be administered as soon as possible after randomisation and preferably not later than 12 h after randomisation.
- m Plasma samples will be taken at baseline (pre-infusion) and at the following time points after start of infusion: 5 min \pm 1 min, 15 min \pm 1 min, 25 min \pm 1 min, 30 min - 1 min (the infusion will not be stopped before the 30-min PK sample has been collected), 45 min \pm 5 min, 1 h \pm 5 min, 1 h 30 min \pm 5 min, 4 h \pm 5 min, 8 h \pm 5 min, and 24 h \pm 2h. In the case of conversion from atrial fibrillation within 90 min from the start of infusion, an additional sample will be taken immediately after conversion.

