- n ECG print-outs: within 15 min before infusion start, at 10 min after infusion start, and, in case of conversion from AF, within 1 min after conversion BUT before infusion stop. Diagnosis of AF (defined as absence of discrete P waves and an irregular ventricular rate) to be confirmed based on a 12-lead ECG. On Day 2 the ECG should be completed 24 h +/- 2 hours after infusion start.
- o Continued assessment to start 30 min before infusion. Holter to stop after the PK sampling at 8 h. Telemetry to continue for minimum 8 h after infusion start.
- p Should be done in all patients; mandatory if not done within 6 months (inclusive) before randomisation.
- q Heart rhythm, LV size, LV area, LVEF, atrial area and size as well as other clinically significant finding results to be provided or requested if available.
- r In case of AF persistence at 90 min after start of infusion, a direct-current electrical cardioversion is to be done within 180 min post-infusion start (200 J biphasic synchronised).
- s Recording of any AEs/SAEs will start after the ICF has been signed. From infusion start, special attention should be paid to AEs related to the central nervous system including tremors.

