8.4 Investigational Products

8.4.1 Investigational Products Administered

Study drugs will either be AP30663 or placebo; both will be administered as an intravenous infusion for 30 min.

Prior to the interim analysis (Part 1 of the study), patients randomised to the AP30663 arm will receive AP30663 at a dose of 3 mg/kg.

The starting AP30663 dose(s) for Part 2 of the study will be determined during DMC review of the interim analysis at the end of Part 1. In Part 2, patients randomised to AP30663 may receive one of the following AP30663 doses: 2, 4, 5, or 6 mg/kg dependent on the results seen for the decision criteria, and the subsequent dose recommended by the DMC.

Patients randomised to the placebo arm will receive matching placebo infusion.

The following instructions apply for intravenous infusion of study drugs:

- The patient should be in (semi-) supine position.
- A large peripheral vein (e.g. antecubital) should be chosen.
- For each patient, the largest clinically feasible cannula size should be used at the discretion of the investigator to avoid local injection site reactions.
- After end of infusion, the intravenous lines should be flushed with 5% glucose solution.

Study drugs must be administered as soon as possible after randomisation and preferably not later than 12 h after randomisation.

Specific detailed instructions on study drug administration and a standardised infusion site assessment are provided in the Study Drug Administration Manual.

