9.3 Day 1 – During Infusion

When all the baseline procedures have been performed and the investigator has confirmed the patient's eligibility for the study, study drug will be administered as a single intravenous infusion for 30 min on Day 1. The following procedures will be performed during infusion on Day 1:

- Administer study drug as intravenous infusion.

¹ Note, if the patient is found eligible, the randomisation should be planned in such a way that all logistics will occur in the protocol-specified timeframe, including timely reconstitution of study drug, infusion start and – if applicable - DC cardioversion in non-responders within 180 min from infusion start.

- Record any AEs that have occurred since the pre-infusion status and any changes in concomitant medication. Special attention should be paid to monitoring for AEs related to the central nervous system including tremors. Please also refer to section 8.2.4.2 for stop of infusion criteria.
- Record vital signs ([semi]supine BP, heart rate, heart rhythm from ECG).
- Collect PK plasma samples 5 min \pm 1 min, 15 min \pm 1 min, 25 min \pm 1 min, and 30 min - 1 min after start of infusion. The infusion should not be stopped before the 30 min - 1 min PK sample has been collected. In the case of conversion from atrial fibrillation during infusion, an additional PK sample will be taken immediately after conversion.
- Perform a 12-lead digital ECG (with ECG print-outs 10 min after infusion start and, in case of conversion from AF, within 1 min after conversion BUT before infusion stop).
- Continue 12-lead Holter monitoring.
- Continue telemetry.

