10.1. Extent of Exposure

Extent of exposure will be summarized by treatment group for duration of infusion .

Duration of infusion will be derived as:

Duration of infusion (in min)= (Stop Time of Study Drug Infusion- Start Time of Study Drug Infusion) – duration of infusion interruption

Extent of exposure (expected total volume to infuse and infused volume) will be summarized by treatment group.

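### The protocol is inconsistent on whether the infusion continues after conversion; if some converters are stopped early, exposure depends on outcome in the safety and PK results by dose

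*Protocol*

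**What the plan says.** **Wording that implies conversion ends the infusion.** Protocol 8.3.4.2 opens its list with "Criteria for stop of drug infusion prior to cardioversion or prior to the infusion duration of 30 min are as follows". Footnote n to the schedule in Protocol 8.1.2, repeated in 9.3, asks for an ECG print-out "in case of conversion from AF, within 1 min after conversion BUT before infusion stop".

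**Wording that states a full 30 minutes.** Protocol 8.4.1 says of AP30663 and placebo that "both will be administered as an intravenous infusion for 30 min", and 9.7 plans the same duration for every patient. Footnote m in 8.1.2 adds that "the infusion will not be stopped before the 30-min PK sample has been collected". Section 9.3 says: "The infusion should not be stopped before the 30 min - 1 min PK sample has been collected". SAP 9.1 repeats the rule. SAP 5.7 names an infusion ended before 30 minutes as noncompliance, among the major deviations. None of these passages makes an exception for converters. The PK passages do foresee conversion, because they ask for one extra sample when it happens.

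**What is reported on exposure.** SAP 10.1 derives infusion duration and adds: "Extent of exposure (expected total volume to infuse and infused volume) will be summarized by treatment group". SAP 10.2 summarises completed infusions and reasons for stopping. In the SAP's index of tables, the exposure table (14.1.5.1) is marked for the DMC and the compliance table (14.1.5.2) is not.

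**The concern.** The trial is meant to identify a dose for later research, and nearly all its summaries are by randomised mg/kg dose. If a site ends the infusion when the patient converts, that patient's delivered dose is set by the outcome: the sooner the conversion, the less drug. Arms that convert more would fall further below their nominal dose.

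The results at stake are those that depend on how much drug was given. Protocol section 6 describes the QTcF effect as related to dose and plasma concentration, and the DMC may close an arm for QTcF or local reactions. The relation of systemic exposure to conversion, QRS and QTcF is a secondary objective, and the correlation of Cmax and AUC with time of conversion is an exploratory endpoint.

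**Working it through.** The plan gives no figure of its own on this point. The check is a reading of the text, followed by simple proportion.

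**Step 1. What can cardioversion mean in 8.3.4.2?** It cannot be the electrical shock. Under 8.1.2 footnote r and 8.4.8.2, that is given only if AF persists 90 minutes after the start, an hour after a 30-minute infusion is over. It must mean conversion during the infusion, set beside 30 minutes as another natural end.

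**Step 2. What does the ECG clause add?** If the infusion always runs to 30 minutes, a tracing within 1 minute of conversion already precedes the stop, unless conversion falls in the last minute. The clause has a wider use only if conversion leads to stopping.

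**Step 3. Set against the explicit statements.**

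| Place | Reading |
|---|---|
| Protocol 8.3.4.2, opening line | conversion ends infusion (implied) |
| Protocol 8.1.2 footnote n; 9.3 (ECG) | conversion ends infusion (implied) |
| Protocol 8.1.2 footnote m; 9.3 (PK); SAP 9.1 | no stop before the 30-min sample (explicit) |
| Protocol 8.4.1; 9.7 | 30 min for all (explicit) |
| SAP 5.7 | earlier stop is noncompliance (explicit) |

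Section 9.3 contains both readings. No sentence expressly orders a stop at conversion, and none says in terms that a converter continues.

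**Step 4. Delivered dose if stopped at conversion.** Inputs: 30-minute duration (8.4.1); constant rate (assumption); conversion minute t (the documents give no distribution, so a range is shown). Delivered share = t/30; mg/kg received = nominal × t/30.

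| t (min) | Share | 3 mg/kg | 5 mg/kg | 6 mg/kg |
|---|---|---|---|---|
| 5 | 17% | 0.50 | 0.83 | 1.00 |
| 10 | 33% | 1.00 | 1.67 | 2.00 |
| 15 | 50% | 1.50 | 2.50 | 3.00 |
| 20 | 67% | 2.00 | 3.33 | 4.00 |
| 25 | 83% | 2.50 | 4.17 | 5.00 |
| 29 | 97% | 2.90 | 4.83 | 5.80 |

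Nominal arms can overlap: 6 × 15/30 = 3 mg/kg and 5 × 18/30 = 3 mg/kg.

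**Step 5. Arm average, as illustration only.** Assume 8/12 convert (the 4 mg/kg arm in Example 1 of Protocol 17.3, which is simulated), a fraction f of them during infusion at a mean of 15 min, and all of those stopped. Mean share = 1 − (8/12) × f × (1 − 15/30). With f = 0.5 this is 1 − 0.167 = 83%; with f = 1 it is 1 − 0.333 = 67%.

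**Step 6. Which analyses are touched?**
- *Largely untouched:* the primary endpoint in the Full Analysis Set, time to conversion, and the interim rules, which use conversion by randomised dose. A stop triggered by conversion comes after the event; only the 1-minute recurrence condition could still be affected.
- *Touched:* QTcF and adverse events by dose; Cmax and AUC by dose level (SAP Figures 14.2.3.6 to 14.2.3.8); AUC0-t and AUC0-0.5 against time to conversion (Figures 14.2.3.10 and 14.2.3.11). In those last plots early conversion would itself lower AUC, so part of the relation would be produced by the stopping.
- *Possibly touched:* relapse within 5 minutes, and sinus rhythm at 3 h, 24 h and 30 days.

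**Step 7. Would the planned tables show it?** Expected volume = weight × dose / 2 mg/mL (Protocol 8.4.2). For 50 to 110 kg that is 75 to 165 mL at 3 mg/kg and 125 to 275 mL at 5 mg/kg, so infused volume alone does not show dose received. The per-patient ratio does: infused/expected = (infused × 2)/(weight × dose), and multiplying by nominal dose gives mg/kg received. SAP 10.1 has both volumes but names neither the ratio nor a split by conversion.

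**The case against.** The strongest reply is that the documents already answer the question. The PK sampling rule appears three times, SAP 5.7 agrees with it, and conversion is not among the stop criteria in 8.3.4.2. That section also excuses a fall in blood pressure or heart rate when conversion is the cause, which would serve little purpose if conversion itself ended the infusion. The ECG clause has an innocent use for last-minute conversions, and detailed instructions sit in a manual outside these documents.

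Much of this stands. The sides are unequal: one is explicit, the other inferred, and it would be wrong to say the plan is silent. But the explicit statements are not absolute, since 8.3.4.2 permits safety stops before 30 minutes, and the wording of 8.3.4.2 and footnote n still points the other way. Even if the manual settles practice, the protocol text remains inconsistent.

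Two further replies also hold in part. Cmax need not fall in proportion to volume, because Protocol section 6 reports that in animals plasma levels reached an apparent steady state well before the infusion ended. The proportional figures therefore describe dose delivered, not Cmax or QTcF. And infusion duration, both volumes, early termination and its reason are recorded, so early stopping could be described afterwards. What is missing is the derived ratio and the split by conversion.

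A reader might infer that sites do in fact differ. Nothing in the documents shows that.

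**Conclusion.** The inconsistency is real and limited. Protocol 8.3.4.2, footnote n and the ECG item in 9.3 imply that conversion ends the infusion; footnote m, the PK item in 9.3, 8.4.1, 9.7 and SAP 5.7 and 9.1 state 30 minutes without exception for converters. If some converters are stopped early, each receives t/30 of the nominal dose, from 17% at 5 min to 83% at 25 min. This assumes a constant rate; conversion times and the share of patients stopped are unknown. Safety, PK and exposure–response results by nominal dose would then carry an exposure that depends on outcome.

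Two stronger conclusions are tempting and not supported. One is that results by nominal dose are not comparable at all: the primary analysis and the interim dose rules rest on conversion, which precedes any such stop. The other is that an early converter gets a third of the dose: that is true only for conversion at minute 10.

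**What to change.** Reconcile Protocol 8.1.2 (footnotes m and n), 8.3.4.2, 8.4.1 and 9.3 with SAP 5.7 and 9.1 into one statement of what happens to the infusion at conversion. This review takes no view on which rule that should be.

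In SAP 10.1, add the delivered fraction (infused/expected volume) or the mg/kg received (infused volume × 2 mg/mL / dosing weight), by arm and by converted during infusion yes/no. Include it in Table 14.1.5.1, which already goes to the DMC.

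The cost is a protocol clarification, one variable derived from data already collected, and one extra table split.

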8.4 Investigational Products

8.4.1 Investigational Products Administered

Study drugs will either be AP30663 or placebo; both will be administered as an intravenous infusion for 30 min.

Prior to the interim analysis (Part 1 of the study), patients randomised to the AP30663 arm will receive AP30663 at a dose of 3 mg/kg.

The starting AP30663 dose(s) for Part 2 of the study will be determined during DMC review of the interim analysis at the end of Part 1. In Part 2, patients randomised to AP30663 may receive one of the following AP30663 doses: 2, 4, 5, or 6 mg/kg dependent on the results seen for the decision criteria, and the subsequent dose recommended by the DMC.

Patients randomised to the placebo arm will receive matching placebo infusion.

The following instructions apply for intravenous infusion of study drugs:

- The patient should be in (semi-) supine position.
- A large peripheral vein (e.g. antecubital) should be chosen.
- For each patient, the largest clinically feasible cannula size should be used at the discretion of the investigator to avoid local injection site reactions.
- After end of infusion, the intravenous lines should be flushed with 5% glucose solution.

Study drugs must be administered as soon as possible after randomisation and preferably not later than 12 h after randomisation.

Specific detailed instructions on study drug administration and a standardised infusion site assessment are provided in the Study Drug Administration Manual.

8.4.2 Identity and Preparation of Investigational Products

AP30663 is a small molecule drug with a molecular weight of [REDACTED]. The drug substance appears as a white to off-white [REDACTED].

The AP30663 drug product is a concentrate for solution for infusion containing 200 mg/mL AP30663. The drug product is provided in a 10 mL glass vial containing 5 mL of AP30663 concentrate. The vial is closed with a coated bromobutyl rubber stopper. The AP30663 drug concentrate is stored in the original container at -15°C to -25°C. The AP30663 concentrate for solution for infusion has the following composition (Table 1):

Table 1 Composition of AP30663 Concentrate for Solution for Infusion

Component	Content	Action
AP30663	1000 mg	Active ingredient
[REDACTED]	[REDACTED]	[REDACTED]
[REDACTED]	[REDACTED]	Solvent

Preparation of the final solution for infusion will be done at the clinical site and is described below.

The AP30663 drug concentrate is diluted with sterile 5% glucose solution for infusion to a concentration of 2 mg/mL prior to administration according to the following procedure:

Vials with the AP30663 drug concentrate intended for preparation of the final solution for infusion will be removed from the freezer and placed at room temperature 30 to 60 min before the start of preparation.

The required amount of 5% glucose solution for injection is transferred to an infusion bag. The respective required amount of AP30663 concentrate is added to the infusion bag. The infusion bag is shaken gently during the addition of the concentrate to ensure that a clear solution is obtained. The final solution for infusion must be stored at room temperature and must be used within 24 h after start of preparation.

The required quantity of the final AP30663 solution for infusion is calculated based on the patient's body weight (determined with clothes but without shoes) rounded to the nearest integer. The following formula will be used for dose calculation:

Body weight [kg] rounded to nearest integer \times intended AP30663 dose [mg] \div 2 mg/mL

The following rule applies: Body weight decimals 0.1 kg to 0.4 kg will be rounded down and 0.5 to 0.9 kg will be rounded up.

Detailed instructions for the preparation and handling of the final AP30663 solution for infusion including a detailed and easily read checklist and a dose calculation nomogram will be provided in the pharmacy manual. Careful training of unblinded site staff with regards to the reconstitution will be conducted.

Placebo solution is not frozen and will be administered as a 5% glucose solution in the same way as AP30663. To ensure blinding, volume and/or weight of the placebo solution will be adjusted to match that of the AP30663 dose provided. Detailed instructions for the preparation and handling of the placebo solution including a detailed and easily read checklist and a dose calculation nomogram will be provided in the pharmacy manual as well.

Specific procedures to ensure blinding are described in [Section 8.4.7](#).

All investigational products will be manufactured and, if applicable, imported according to the relevant regulatory requirements.

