11.1.3 Efficacy Variables

Definition of Primary Efficacy Endpoint

The primary efficacy endpoint is defined as the proportion of patients who have converted from AF within 90 min from the start of infusion, and subsequently have no AF recurrence within 1 min of conversion from AF.

Definition of Secondary Efficacy Endpoints

- The time to conversion from AF from start of infusion.
- The proportion of patients with relapse of AF within 5 min (IRAF) after pharmacological or DC cardioversion.
- The proportion of patients in SR at $3\text{ h} \pm 1\text{ h}$ after start of infusion.
- The proportion of patients in SR at $24\text{ h} \pm 2\text{ h}$ after start of infusion.
- The proportion of patients in SR at $30\text{ days} \pm 5\text{ days}$ after start of infusion.

Methods of Analysis

For the analysis of the primary endpoint (proportion of patients who have cardioversion within 90 min from the start of infusion) a Bayesian model will be utilised. The prior probability of success at a dose, d , is modelled with a $P_d \sim \text{Beta}(1,1)$ prior (uniform) for each dose. Across both Parts 1 and 2 of the study, the potential doses (arms) in the trial are $d = 0$ (placebo), 2, 3, 4, 5, and 6 (all mg/kg dose units).

Let X_d be the number of successes and N_d be the number of observations at dose d . The posterior distribution is calculated for each dose independently using a Beta posterior distribution,

$$P_d \sim \text{Beta}(1 + X_d, 1 + N_d - X_d).$$

The adaptive design utilises the probability that the response rate at a dose is greater than a 65% success rate. This is ($P_d > 0.65$), for each dose d .

This modelling will occur for each interim analysis, and at the final analysis as primary method. At the conclusion of the study, each AP30663 dose will be considered to be superior to placebo, if the posterior probability of AP30663 dose has a higher success rate than placebo is greater than 0.95.

Further to the above, for the final analysis the primary endpoint will also be analysed by means of a logistic regression model. Relevant covariates at baseline may be added into the model after reviewing baseline imbalances.

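### The only dose-calculation formula (protocol 8.4.2) labels its dose term in mg although study doses are set in mg/kg, so as printed it does not return a volume

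*Protocol*

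**What the plan says.** Protocol 8.4.2 states that "The required quantity of the final AP30663 solution for infusion is calculated based on the patient's body weight", and then gives the rule: "Body weight [kg] rounded to nearest integer \times intended AP30663 dose [mg] \div 2 mg/mL". The product is diluted "to a concentration of 2 mg/mL prior to administration", which is where the divisor comes from. Protocol 8.4.6 sends the reader to 8.4.2 for individual weight-based doses, and neither the protocol nor the SAP contains another dose formula or a worked volume.

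The doses themselves are set per kilogram. In Part 1, "patients randomised to the AP30663 arm will receive AP30663 at a dose of 3 mg/kg". In Part 2 a patient may receive "one of the following AP30663 doses: 2, 4, 5, or 6 mg/kg" (8.4.1, repeated in 8.4.5). Protocol 11.1.3 lists the active arms as "2, 3, 4, 5, and 6 (all mg/kg dose units".

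Four other provisions bear on the point:

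- Protocol 8.4.2 matches the placebo volume and/or weight to the active dose. It refers detailed preparation to a pharmacy manual with a checklist and a nomogram, and requires training of the unblinded staff.
- Protocol 8.4.3 supplies one 500 mL bag of 5% glucose per kit.
- Protocol 8.4.9 requires the dose calculation to be noted in the medical file and the eCRF.
- SAP 10.1 summarises the expected total volume and the infused volume as extent of exposure.

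**The concern.** The formula has two patient-level inputs, "Body weight [kg] rounded to nearest integer" and "intended AP30663 dose [mg"]. If the second is in mg, it is a total dose that already contains body weight, and multiplying by weight again makes no sense dimensionally. If it is meant per kilogram, the printed unit is wrong. As labelled, the formula cannot be reconciled with 8.4.1, 8.4.5 and 11.1.3.

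This matters because 8.4.2 is the protocol's operative rule for how much solution each patient gets, and the placebo volume is matched to it. Anyone building a worksheet, a nomogram or an eCRF derivation of expected volume from the protocol alone has only this line to work from.

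**Working it through.** **Inputs**

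- Body weight *W*: 50 to 110 kg (protocol 8.3.2, inclusion criterion 5).
- Dose level *d*: 2, 3, 4, 5 or 6 mg/kg (8.4.1, 11.1.3).
- Concentration of the final solution: 2 mg/mL (8.4.2).
- Vial content: 1000 mg (8.4.2, Table 1). Glucose bag: 500 mL (8.4.3).

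The documents give no worked volume, so there is no stated figure to reproduce.

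**Units**

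- As printed: kg × mg ÷ (mg/mL) = kg·mL. This is not a volume.
- With the dose term in the unit used for the study arms: kg × (mg/kg) ÷ (mg/mL) = mL.

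**Size under the two ways of filling in the formula**

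- Assigned level entered: *V* = *W* × *d* ÷ 2.
- Total dose in mg entered: *V′* = *W* × (*W* × *d*) ÷ 2.
- Ratio: *V′* ÷ *V* = *W*, whatever the dose level.

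| *W* (kg) | *d* (mg/kg) | Total dose (mg) | Level entered (mL) | Total mg entered (result read as mL) | Ratio |
|---|---|---|---|---|---|
| 50 | 2 | 100 | 50 | 2,500 | 50 |
| 50 | 3 | 150 | 75 | 3,750 | 50 |
| 80 | 3 | 240 | 120 | 9,600 | 80 |
| 110 | 3 | 330 | 165 | 18,150 | 110 |
| 110 | 6 | 660 | 330 | 36,300 | 110 |

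Over all eligible weights and planned doses, the formula gives 50 to 330 mL when the level is entered and 2,500 to 36,300 when a total in mg is entered.

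**Would the larger figure pass unnoticed?** The smallest misread result, 2,500 mL, is five times the 500 mL bag. At 2 mg/mL it contains 5,000 mg, or 5 vials. At 80 kg and 3 mg/kg, 9,600 mL contains 19,200 mg, or 19.2 vials, to be given in 30 minutes. The largest, 36,300 mL, contains 72,600 mg, or 72.6 vials. When the level is entered, every patient needs less than one vial (at most 660 mg).

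**The case against.** The strongest reply is that this is an incomplete unit label on a formula that works. The protocol uses the word dose for the assigned level, and it never asks anyone to compute a per-patient total in mg before using 8.4.2; the formula is itself the conversion from weight to volume. Someone who enters 3 for the 3 mg/kg arm at 80 kg gets 120 mL. The checklist, nomogram and staff training add protection, and nothing in the documents suggests that the nomogram carries the same slip.

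Most of this stands. A reader might infer from the factor of 50 to 110 that the protocol instructs a gross overdose. The documents do not support that: it takes a separate calculation that the protocol does not call for, and the result could not be prepared from the kit as described.

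A reader might also infer that the SAP's compliance or efficacy results are affected. They are not shown to be. SAP 10.2 bases compliance on completed infusions, interruptions and reasons for stopping, without using expected volume. SAP 10.1 uses expected volume for exposure only, gives no derivation for it and does not link it to 8.4.2. The interim decision rules and the primary analysis use the arm and the conversion outcome, not the infused volume.

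What does not fall away is the contradiction itself. The line is the stated rule for dose calculation, its bracketed unit conflicts with 8.4.1, 8.4.5 and 11.1.3, and the pharmacy manual that might settle the matter is not among the documents.

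**Conclusion.** The point holds as a unit error in an operative rule. As printed, the 8.4.2 formula returns kg·mL and contradicts the mg/kg doses stated elsewhere in the protocol. It returns a volume, 50 to 330 mL across the planned range, only if the dose term is per kilogram. The inflation by a factor of 50 to 110 is exact arithmetic, but it is conditional on someone entering a total dose in mg.

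The realistic consequence is a wrong worksheet, nomogram or expected-volume record that has to be caught and corrected. A silent overdose is not a credible reading, given the bag size, the vial content and the preparation safeguards. The correction is worth making because the formula governs preparation of an intravenous product in a study with several dose arms.

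Two assumptions apply: that the signed protocol prints the same bracketed unit, and that the pharmacy manual's units are unknown, neither right nor wrong.

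**What to change.** Reconcile the unit label of the dose term in protocol 8.4.2 with the dose units in 8.4.1 and 8.4.5, so that the formula returns mL. A worked example beside the formula would let staff check the units at a glance.

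Then confirm that the pharmacy manual's nomograms and checklists, for active and for placebo, use the same units. Confirm the same for the expected total volume summarised in SAP 10.1, and state in the SAP or the eCRF specification where that volume comes from.

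The cost is one unit label and a short document check. Nothing changes in the design, the sample size, the decision rules or the analysis, and no dose is judged or proposed here.
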